5.3. Vital Signs, Weight, and BMI

Descriptive statistics (N, mean, median, minimum, and maximum) for values and changes from baseline at each time point during each induction phase (DB and OL) will be presented for temperature, systolic blood pressure, diastolic blood pressure, pulse rate, respiratory rate, oxygen saturation, weight, and BMI. In addition, descriptive statistics of pulse rate and blood pressure (systolic and diastolic) values, changes and percent changes from predose will be provided for each dosing day. These summaries will also be provided by hypertension status (defined in [Table 2](#), Yes/No). Descriptive statistics for maximum increases and maximum percent increase from predose will be provided for each dosing day. Frequency distributions of maximum percent change increase from predose and time of maximum percent change increase will also be presented. Note that if the maximum value within a phase occurs at multiple time points, the earliest time point is selected.

The proportion of subjects who have a treatment-emergent abnormality, as defined in [Table 5](#) below, during each induction phase will be presented. Both the double-blind/open-label baseline and the predose assessment will be used to determine abnormal values. A listing of subjects meeting any of the criteria will also be provided for each induction phase.

Table 5: Treatment-Emergent Abnormality Categories for Vital Signs

| Vital Parameter | Postbaseline value outside of normal limit if: | |
|----------------------|--|--|
| | Abnormally low | Abnormally high |
| Pulse (bpm) | A decrease from baseline of ≥ 15 to a value ≤ 50 | An increase from baseline of ≥ 15 to a value ≥ 100 |
| Systolic BP (mm Hg) | A decrease from baseline of ≥ 20 to a value ≤ 90 | An increase from baseline of ≥ 20 to a value ≥ 180 |
| Diastolic BP (mm Hg) | A decrease from baseline of ≥ 15 to a value ≤ 50 | An increase from baseline of ≥ 15 to a value ≥ 105 |

The proportion of subjects who experienced acute hypertension (systolic BP \geq 180 or diastolic BP \geq 110) at any time during the study will be summarized by analysis phase, treatment group and hypertension status.

Mean (+/-SE) values for systolic BP, diastolic BP and pulse rate will be presented graphically over each induction phase by treatment group and hypertension status. In addition, for subjects with hypertension who receive antihypertensive medication, the same graphs will be summarized by medication type (beta-blockers, all other agents).

A listing of subjects with oxygen saturation less than 93% will be provided.

5.4. Electrocardiogram

ECG variables that will be analyzed include heart rate, RR, PR interval, QRS interval, QT interval and QTc intervals. The corrected QT (QTc) intervals will include QTcB (Bazett) and QTcF (Fridericia).

Baseline ECG is defined as the average of all ECG results collected up to and including the day of the first dose of study medication. This baseline will be used as the baseline for change summaries and to determine abnormal values during each induction phase (DB and OL).

The maximum postbaseline value during each induction phase will be computed for each ECG parameter using data from both scheduled and unscheduled visits.

Summary tables for observed values and changes from baseline will be presented by treatment group at each time point during each induction phase.

The frequency of treatment-emergent abnormalities will be tabulated and presented for each induction phase. The identification of treatment-emergent abnormal ECG values is based on the postbaseline value (a value occurring after the first study drug administration) being out of range while the baseline value is either missing or within the limits given in [Table 6](#). If postbaseline ECG results are above the upper limits (abnormally high) and the baseline value is below the lower limits (abnormally low), then the postbaseline abnormality will also be considered treatment-emergent. The same applies to the postbaseline value being below the lower limits (abnormally low) with the baseline value being above the upper limits (abnormally high). Abnormal ranges for the HR, PR, QRS and QT intervals are given in [Table 6](#).

Table 6: Limits for HR, PR, QRS and QT Interval Abnormality

| ECG parameter | Abnormally Low | Abnormally High |
|---------------------|----------------|-----------------|
| HR (bpm) | ≤ 50 | ≥ 100 |
| PR interval (msec) | -- | ≥ 210 |
| QRS interval (msec) | ≤ 50 | ≥ 120 |
| QT interval (msec) | ≤ 200 | ≥ 500 |

Based on the maximum QTc value for each subject during a given phase (separate for each QTc correction) the incidence of abnormal QTc values and changes from baseline will be summarized by treatment group. Criteria for abnormal corrected QT values and changes from baseline are

given in Table 7 and are derived from the ICH E14 Guidance³ (the same criteria apply to all QT corrections).

Table 7: Criteria for Abnormal QTc Values and Changes From Baseline

| Parameter | Classification | Criteria |
|---------------------------------------|----------------|-------------|
| Clinically Significant QTc Value | No | ≤500 |
| | Yes | >500 |
| QTc change from baseline ^a | No concern | ≤30 |
| | Concern | >30 – 60 |
| | Clear concern | > 60 |
| QTc value | Normal | ≤450 |
| | > 450 – 480 | >450 - ≤480 |
| | > 480 – 500 | >480 – ≤500 |
| | > 500 | > 500 |

These criteria are based on ICH E14 Guideline

^a Baseline is defined as the average predose.

The proportion of subjects with treatment emergent abnormalities will be presented for each induction phase. A listing of subjects with abnormalities will also be provided.

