Visit number	1.1 ^b	2.1 ^b	2.2	2.3	3.1 ^a	3.2	3.3	3.4	3.5	3.6	3.7	3.8	3.9	3.10 ^m	EW ^c	
Study Week	Within 4 weeks of Day P1	-6	-4	-2	1			2		3		4			—	
Study day	-70 (P-28 to P-1)	-42 (P1)	-28 (P15)	-14 (P29)	1 (P43) Prerandomization Postrandomization		2	4	8	11	15	18	22	25	28	EW
Clinic visit window (days)		-3	±3	±3	—	—	—	±1	±1	±1	±1	±1	±1	±1	±1	—
Remote MADRS interview window (in days; relative to Study day [not including visit window])		-3	±3	±3	—	—	—	—	-2 ^d	—	-2 ^d	—	-2 ^d	—	-2 ^{d,p}	—
Clinic visit (C) or remote MADRS interview only (RM)		C	C	C	C		RM	C	C	C	C	C	C	C	C	C
Ongoing Subject Review																
Concomitant therapy	X	X	X	X	X	X		X	X	X	X	X	X	X	X	X
Adverse events	X	X	X	X	X	X		X	X	X	X	X	X	X	X	X

Footnotes:

Note: On intranasal dosing days, time 0 is defined as the time of the first intranasal spray. Therefore, postdose time points are referenced from this.

- Visit 3.1 Prerandomization must coincide exactly on the same day as Visit 3.1 Postrandomization. All subjects who will be randomized and enrolled in the double-blind induction phase must meet all of the inclusion criteria and none of the exclusion criteria at Visit 3.1 Prerandomization. After randomization, all subjects will proceed to Visit 3.1 Postrandomization.
- If clinically indicated, cross tapering is allowed.
- If a subject withdraws before the end of the double-blind induction phase (ie, before completing Visit 3.10/Day 28) for reasons other than withdrawal of consent, an EW Visit should be conducted within 1 week of the date of discontinuation, followed by the follow-up phase. If the EW Visit is conducted on the same day as a scheduled visit, duplicate assessments are not required.
- MADRS assessment should be conducted at predose.
- Predose (if/when performed on intranasal dosing days). With the exception of postdose assessments, subject-reported outcome assessments should be administered before all other study-related procedures during a clinic visit.
- Postdose vital signs will be performed at 40 minutes, 1 hour, and 1.5 hours postdose. Please refer to Section 6.3.1 for guidance for blood pressure monitoring on intranasal dosing days.

-
- g. Twelve-lead ECG will be performed at $t=1$ hour postdose at Visit 3.1 Postrandomization. Twelve-lead ECG will be performed at $t=1$ hour postdose at Visits 3.4 to 3.9 (only at the time points indicated), but no predose ECGs are required at Visits 3.4 to 3.9. A time window of ± 15 minutes is permitted.

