Physical examination ^b	X		X		X			X	X	X
Vital signs: blood pressure, pulse, respiratory rate, temperature ^b	X	X	X	X	X	X	X	X		X
Vital signs (postdose): blood pressure, pulse, respiratory rate ^c	X	X	X	X	X	X	X	X		
Weight ^b	X				X				X	X
12-lead ECG ^d	X				X			X		X
C-SSRS: Since last visit version ^b	X	X	X	X	X	X	X	X	X	X
MOAA/S and pulse oximetry ^e	X	X	X	X	X	X	X	X		
BPRS+ ^f	X	X	X	X	X	X	X	X		
CADSS ^f	X	X	X	X	X	X	X	X		
CGADR ^g	X	X	X	X	X	X	X	X		
PWC-20 ^b								X		X
Efficacy Assessments (Clinician)										
MADRS (7-day recall; performed by independent, remote raters)	X		X		X		X		X	X
CGI-S ^b	X		X		X		X		X	X

	Open-label Induction Phase (Visit number; 5.1-5.10, Study week; OL1-OL4, Study day; OL1-OL28)									
Visit number	5.1	5.3	5.4	5.5	5.6	5.7	5.8	5.9	5.10	EW ^a
Study Week	OL 1		OL 2		OL 3		OL 4			—
Study day	OL 1 ⁱ	OL 4	OL 8	OL 11	OL 15	OL 18	OL 22	OL 25	OL 28	EW
Clinic visit window (days)	—	±1	±1	±1	±1	±1	±1	±1	±1	—
Clinical Laboratory Assessments										
Hematology, chemistry ^b	X								X	X
Urinalysis ^b	X				X				X	X
Serum pregnancy test	X								X	X
Urine pregnancy test ^b					X					
Pharmacokinetics										
Blood collection ^h								X		
Ongoing Subject Review										
Concomitant therapy	X	X	X	X	X	X	X	X	X	X
Adverse events	X	X	X	X	X	X	X	X	X	X

Footnotes:

Note: On intranasal dosing days, time 0 is defined as the time of the first intranasal spray. Therefore, postdose time points are referenced from this.

- If a subject withdraws before the end of the open-label induction phase (ie, before completing Visit 5.10/Day OL28) for reasons other than withdrawal of consent, an EW Visit should be conducted within 1 week of the date of discontinuation, followed by the follow-up phase. If the EW Visit is conducted on the same day as a scheduled visit, duplicate assessments are not required.
- Predose (if/when performed on intranasal dosing days).
- Postdose vital signs will be performed at 40 minutes, 1 hour, and 1.5 hours postdose. Please refer to Section 6.3.1 for guidance for blood pressure monitoring on intranasal dosing days.
- Twelve-lead ECG will be performed at t=1 hour postdose at Visit 5.1 to 5.10 (only at the time points indicated), but no predose ECGs are required at Visits 5.1 to 5.10. A time window of ±15 minutes is permitted.
- The MOAA/S will be performed every 15 minutes from predose to t=+1.5 hours postdose. Pulse oximetry will be performed every 15 minutes from predose to t=1.5 hours postdose.

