2.2. Baseline and End Point

Baseline is defined for each parameter/assessment.

- Baseline (DB): The last assessment before receiving the first dose of intranasal study medication in the double-blind induction phase.

- Baseline (OL): The last assessment before receiving the first dose of intranasal study medication in the open-label induction phase.

Baseline (DB) will be used for DB induction phase, DB follow-up phase and posttreatment (PT) phase. Baseline (OL) will be used for OL induction phase and OL follow-up phase.

The ‘End Point (DB)’ value is defined as the last post baseline assessment value during the double-blind induction phase.

The ‘End Point (OL)’ value is defined as the last post baseline assessment value during the open-label induction phase.

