5. SAFETY

All safety summaries for induction phases will be based on the safety analysis sets described in Section 2.4.3. Safety summaries for the follow-up phases will be based on the follow-up analysis sets described in Section 2.4.4.

Unless specified otherwise, Baseline (DB) will be used for DB induction phase and DB follow-up phase. Baseline (OL) will be used for OL induction phase and OL follow-up phase.

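### The SAP 5.4 ECG baseline is not limited to predose recordings, so as written it includes the Day 1 one-hour postdose ECG, contradicts the SAP's other baseline rules and can suppress treatment-emergent ECG flags

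*SAP*

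**What the plan says.** SAP 5.4 sets its own ECG baseline: "the average of all ECG results collected up to and including the day of the first dose of study medication". It then fixes the scope: "This baseline will be used as the baseline for change summaries and to determine abnormal values during each induction phase (DB and OL"). The same section treats a postbaseline ECG as "a value occurring after the first study drug administration".

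Footnote g of protocol Time and Events Schedule 1 places an ECG at 1 "hour postdose at Visit 3.1 Postrandomization", which is Day 1. Screening and Day 1 before randomization are the other scheduled ECGs up to that point. For the open-label phase, the ECG footnote of Schedule 3 says "no predose ECGs are required at Visits 5.1 to 5.10".

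Other baseline rules bear on the same data:

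- SAP 2.2, general rule for the double-blind phase: "The last assessment before receiving the first dose of intranasal study medication in the double-blind induction phase".
- SAP 5: "Unless specified otherwise, Baseline (DB) will be used for DB induction phase and DB follow-up phase", with the open-label baseline used for the open-label phases.
- SAP Table 1, ECG rows: the double-blind baseline window is Day 1 or earlier and predose, and the Day 1 one-hour ECG is a separate time point. There is no open-label ECG baseline row.
- SAP Table 7, footnote a, attached to the QTc change row: "Baseline is defined as the average predose".

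**The concern.** The definition in SAP 5.4 stops at a calendar day, not at the dose, and a postdose ECG is scheduled on that day. Read as written, the Day 1 one-hour ECG is both part of baseline and a postbaseline value.

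Two programmers could each follow the SAP and produce different ECG tables. The literal reading would affect:

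- changes in heart rate, RR, PR, QRS and QT;
- QTc change summaries outside Table 7;
- the treatment-emergent flags of Table 6;
- the QTcF change in the PK/PD plots of SAP 6.2.

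The Table 6 flags are the most exposed. A high value counts as treatment-emergent only if baseline is missing, within limits or abnormal in the opposite direction. A large first-dose effect can push the literal baseline over the limit and so remove its own flag.

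**Working it through.** **Which ECGs enter.** The scheduled ECGs up to the end of Day 1 are screening, Day 1 predose and Day 1 one hour postdose. Exclusion criterion 11 adds sets of three ECGs when QTcF is prolonged, so the number of predose ECGs can exceed two.

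**Algebra.** Let n be the number of predose ECGs, m their mean, q the Day 1 one-hour value and x a later value.

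- Literal baseline = (n·m + q)/(n + 1) = m + w(q − m), with w = 1/(n + 1)
- Day 1 one-hour change = (1 − w)(q − m)
- Later change = (x − m) − w(q − m)

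| Predose ECGs assumed | n | w | Day 1 one-hour change reported at |
|---|---|---|---|
| Scheduled only | 2 | 1/3 | 67% |
| Screening initial + 3 repeats, one on Day 1 | 5 | 1/6 | 83% |
| Initial + 3 repeats on both occasions | 8 | 1/9 | 89% |

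The last two rows assume that repeats are additional to the initial ECG and are all in the database. If the initial ECG is one of the three, n is 4 or 6 and w is 20% or 14%, inside the same range.

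**Heart-rate shift.** The documents give no effect size. Assuming a Day 1 one-hour rise of 3, 6 or 9 bpm, later changes shift by −1, −2 or −3 bpm at w = 1/3, and by −0.3, −0.7 or −1.0 bpm at w = 1/9.

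**Table 6 heart-rate flag (high is 100 or more).** With m below 100, the flag is lost when (n·m + q)/(n + 1) ≥ 100, that is, q ≥ 100(n + 1) − n·m.

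| Mean predose HR | q needed, n = 2 | q needed, n = 5 |
|---|---|---|
| 85 | 300 − 170 = 130 | 600 − 425 = 175 |
| 90 | 300 − 180 = 120 | 600 − 450 = 150 |
| 95 | 300 − 190 = 110 | 600 − 475 = 125 |

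Example with assumed values: predose 90 and 90, one hour 125. The literal baseline is (90 + 90 + 125)/3 = 101.7, so 125 is not flagged, nor is any later value of 100 or more. Against the predose mean of 90, it is flagged.

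**QTc change categories.** These are affected only if SAP 5.4 is taken to override footnote a. At w = 1/3, a Day 1 one-hour change would then have to exceed 30/(2/3) = 45 msec, or 60/(2/3) = 90 msec, to be classed above 30 or 60.

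**Whether another rule settles it.** SAP 5 yields where a section specifies otherwise, and 5.4 does so. Footnote a reaches only the QTc change row. In the open-label phase, falling back on SAP 2.2 would normally select the double-blind Day 25 ECG, which is also one hour postdose, because no ECG is scheduled in the posttreatment phase.

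**The case against.** The best reply is that predose was plainly intended and that the rest of the SAP says so. Table 1 has a predose window and gives the one-hour ECG its own row. SAP 2.3 does not let a visit assigned to one window be reused for a later time point. SAP 5.4 itself makes the one-hour ECG postbaseline. Footnote a can be read as restating the same averaged baseline. Protocol 9.1.5 and the QTcF withdrawal rule in protocol 10.2 also treat baseline as predose. On this view the defect is a missing word.

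That is probably right about intent. It does not remove the conflict, because 5.4 expressly sets its own baseline for change summaries and abnormal values in both phases. The other rules also disagree among themselves: SAP 2.2 takes the last value, footnote a an average.

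The objections about consequence carry more weight:

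- At w = 1/3 the flag thresholds need Day 1 rises of 45, 30 or 15 bpm, well above the assumed mean effects.
- SAP 5.3 summarizes pulse change from predose on each dosing day. Its Table 5 flag (a rise of at least 15 to 100 or more) is judged against both phase baseline and predose. A pulse going from 90 to 125 would be caught there.
- The absolute QTc categories do not use baseline.
- The QTcF PK/PD plots use Day 25 only, so they carry the baseline shift but not the damped Day 1 change.

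These points limit the harm without making the ECG tables correct.

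**Conclusion.** The concern holds. As written, SAP 5.4 puts a scheduled postdose ECG into baseline and contradicts the SAP's predose rules. On scheduled ECGs the weight is 1/3, falling to 1/9 under the repeat-ECG assumptions above.

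A direction of bias is supported only for heart rate, where protocol 1.1.2.3 reports transient increases: changes would be understated in the esketamine arms. The bpm figures are assumptions. For QTc and PR, the rationales of protocol Amendments 3 and 5 report no esketamine effect, so no between-arm bias in means is claimed. Individual Day 1 one-hour changes are damped in all arms, and individual flags can change.

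This is a descriptive safety analysis. The primary endpoint, significance level and sample size are not affected. It should still be corrected, because following the stated rule gives wrong changes and can drop safety flags.

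**What to change.** In SAP 5.4, define baseline ECG as the mean of all ECGs recorded before the DB start date/time, which SAP 2.1.2 already defines. State that this one baseline serves all ECG change summaries, the Table 6 flags, Table 7 and the QTcF changes in SAP 6.2, in both induction phases. Record it in SAP 2.2 as an ECG-specific exception to the last-assessment rule and to the separate open-label baseline. Align the ECG rows of Table 1, including the open-label rows.

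This keeps the SAP's averaging and resolves both the predose conflict and the average-versus-last conflict. The cost is one sentence in 5.4, a note in 2.2, the Table 1 alignment and one date/time filter in the derivation program. No new data are needed.

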5.5. Other Safety Parameters

5.5.1. Columbia Suicide Severity Rating Scale (C-SSRS)

The C-SSRS (Columbia Suicide Severity Rating Scale) is a low-burden measure of the spectrum of suicidal ideation and behavior that was developed in the National Institute of Mental Health Treatment of Adolescent Suicide Attempters Study to assess severity and track suicidal events through any treatment.⁹ It is a semi structured clinician-administered questionnaire designed to solicit the occurrence, severity, and frequency of suicide-related ideation and behaviors during the assessment period. Using the C-SSRS, potentially suicide-related events will be categorized using the following scores:

Suicidal Ideation (1-5)

1. Wish to be Dead
2. Non-specific Active Suicidal Thoughts
3. Active Suicidal Ideation with Any Methods (Not Plan) without Intent to Act
4. Active Suicidal Ideation with Some Intent to Act, without Specific Plan
5. Active Suicidal Ideation with Specific Plan and Intent

Suicidal Behavior (6-10)

6. Preparatory Acts or Behavior
7. Aborted Attempt
8. Interrupted Attempt
9. Actual Attempt (non-fatal)
10. Completed Suicide

If no events qualify for a score of 1 to 10, a score of 0 will be assigned (0= “no event that can be assessed on the basis of C-SSRS”). Higher scores indicate greater severity.

The summaries of the C-SSRS outcomes will be applied for subjects who have at least 1 postbaseline C-SSRS measurement and a pretreatment C-SSRS assessment (assessment at Baseline visit).

A frequency distribution at each scheduled time point will be provided. Shifts from the baseline visit to the most severe/maximum score during each analysis phase (DB induction, DB follow-up, PT, OL induction and OL follow-up) will be summarized.

The maximum score assigned for each subject will also be summarized into one of three broad categories: No suicidal ideation or behavior (0), Suicidal ideation (1-5), Suicidal behavior (6-10). Shifts from the baseline visit to the maximum category during each analysis phase will be summarized.

5.5.2. Clinician Administered Dissociative States Scale (CADSS)

The CADSS (Clinician Administered Dissociative States Scale) is an instrument for the measurement of present-state dissociative symptoms, and is administered to assess treatment-emergent dissociative symptoms.² The CADSS comprises 23 subjective items and participant’s responses are coded on a 5-point scale (0 = “Not at all”, 1 = “Mild”, 2 = “Moderate”, 3 = “Severe” and 4 = “Extremely”). The CADSS is divided into 3 components using the scoring method shown in [Table 8](#).

Table 8: CADSS Scoring

| Component | Questions | Range |
|-------------------|---|-------|
| Depersonalization | Sum of 3, 4, 5, 6, 7, 20, 23 | 0-28 |
| Derealization | Sum of 1, 2, 8, 9, 10, 11, 12, 13, 16, 17, 18, 19, 21 | 0-52 |
| Amnesia | Sum of 14, 15, 22 | 0-12 |
| Total Score | Sum of 1 through 23 | 0-92 |

For the total score and each component, a higher score represents a more severe condition. If any response is missing the total score is set to missing. The CADSS is measured prior to each dose, at 40 minutes, and at 1.5 hours postdose during each induction phase (DB and OL).

Descriptive statistics (N, mean, median, minimum, and maximum) of the total scores and component scores, changes from the predose at each time point, and the proportion of subjects with an increase in CADSS total score from the predose value at any time during the study will be summarized. Mean (SE) CADSS values will be presented graphically for each dosing day.

5.5.3. Brief Psychiatric Rating Scale (BPRS)

The Brief Psychiatric Rating Scale (BPRS) is an 18-item rating scale which is used to assess potential treatment-emergent psychotic symptoms. The BPRS assesses a range of psychotic and affective symptoms rated from both observation of the subject and the subject's own report. Only the four-item positive symptom subscale (BPRS+) will be used in the study to assess treatment-emergent psychotic symptoms. The BPRS+ consists of: suspiciousness, hallucinations, unusual

thought content and conceptual disorganization. Each symptom is rated on a scale of 0 to 6 as follows: 0: not present, not evident or absent; 1: very mild; 2: mild; 3: moderate; 4: moderate severe; 5: severe; or 6: extreme. A total score will be derived by summing the individual items, with a range of 0 to 24 with a higher score representing a more severe condition.

The BPRS+ is measured prior to each dose, at 40 minutes, and at 1.5 hours postdose during each induction phase (DB and OL).

Descriptive statistics (N, median, minimum, and maximum) of the total scores at each time point, the change from the predose at each time point, and the proportion of subjects with an increase in BPRS+ from the predose value at any time during the study will be summarized. The proportion of subjects with a total score of 3 or more at any time during the study will also be provided. Mean (SE) BPRS+ values will be presented graphically for each dosing day.

